6.2.2.3 Hamilton Rating Scale for Depression (HAM-D-17)

The HAM-D-17 is a 17-item observer-rated scale that assesses depressive symptoms ([Hamilton 1960](#)) each of which is rated from 0 to 2 to 0 to 4, where 0 is none/absent. Depressive symptoms include depressed mood, feelings of guilt, suicide, insomnia-early, insomnia-middle, insomnia-late, work and activities, retardation, agitation, anxiety psychic, anxiety somatic, somatic symptoms-gastrointestinal, somatic symptoms-general, genital symptoms, hypochondriasis, loss of weight, loss of insight, diurnal variation,

depersonalization and derealization, paranoid symptoms, and obsessional symptoms. The first 17 items contribute to the total score. The HAM-D-17 will be performed during the screening (Visit 1) and randomization visits (Visit 2) to determine whether the patient meets the severity inclusion criterion of a total score of ≥ 24 .

6.2.2.4 Clinical Global Impression of Severity (CGI-S)

The CGI scale is a 3-part, clinician-administered scale that assesses global illness severity and change (Guy 1976). For inclusion criteria and to examine the effects of the IP, the first part, Severity of Illness (CGI-S) will be used. This is a single score, rated on a scale from 1 to 7, to reflect the patient's current clinical state.

A CGI-S score of 1 indicates that a patient is "Normal, not ill" and a score of 7 indicates that a patient is "Among the most extremely ill patients." The CGI-S should be administered at designated visits prior to the infusion.

6.2.2.5 The Mini-International Neuropsychiatric Interview (MINI)

The Mini-International Neuropsychiatric Interview (Sheehan et al 1998) is a short, structured diagnostic interview developed jointly by psychiatrists and clinicians in the United States and Europe for Diagnostic and Statistical Manual of Mental Disorders, 4th edition (DSM-IV) and International Classification of Diseases and Related Health Problems (10th edition) (ICD-10) psychiatric disorders. With an administration time of approximately 15 minutes, it was designed to meet the need for a short and accurate structured psychiatric interview for multicenter clinical studies and epidemiology studies. The MINI Version 6.0.0 will be used in this study.

6.2.2.6 Columbia-Suicide Severity Rating Scale (C-SSRS)

The C-SSRS is a unique, simple and short method of assessing both behavior and ideation that tracks all suicidal events, and provides a summary of suicidality (Posner et al 2007). It assesses the lethality of attempts and other features of ideation (frequency, duration, controllability, reasons for ideation and deterrents), all of which are significantly predictive of completed suicide. The C-SSRS must be administered after each infusion and prior to discharging the patient from the clinic.

6.2.2.7 Psychiatric and family history

For psychiatric and family history, information is collected on previous psychiatric episodes of the patient and also includes a brief family history of psychiatric disorder and alcohol abuse/dependence. This form is completed once at the screening visit. If additional information about family history is obtained during the course of the study, this form may be updated to reflect the most accurate family history information known to the investigator.

6.2.3 Recording of data

All clinical ratings and other data collected for this study will be recorded on specifically designed eCRFs.

6.3 Efficacy

6.3.1 Sequence of clinical rating assessments

Table 4 lists all clinical and laboratory assessments to be conducted at the screening visit and all subsequent visits. The following “priority order” among clinical ratings will be in effect for all visits after the screening visit.

Pre-infusion

- QIDS-SR-16
- S-STS (self report)
- MADRS
- HAM-A
- SDS
- CGI-S
- CGI-I
- CogState

Post-infusion

- C-SSRS (conducted by the investigator after reviewing and signing S-STS during visits when both instruments are used)
- CADSS

6.3.2 Instruments

The following is a description of all clinical rating instruments used to measure efficacy not described above in Section 6.2.2. All ratings will be made by the investigator or delegate, according to the schedule of events in Table 4. Patient-reported outcome scales include: QIDS-SR-16, SDS (efficacy), and S-STS, CADSS (safety).

To ensure consistency throughout the study, all site personnel (eg, physician, PhD, RN, or other healthcare professional skilled and experienced in the care of this patient population) administering the MADRS, HAM-D, C-SSRS, HAM-A, CADSS, CGI-I, and CGI-S, will receive training in conducting these assessments. In addition, certification will be required for MADRS, CGI, and C-SSRS scale administration (prior to rating these scales for this study). The back-up rater must meet the same qualifications as the primary rater and be authorized by the PI and approved by AstraZeneca or representative to conduct the ratings.

The scores in each of the scales will be recorded on the appropriate sections of the eCRF. Signs and symptoms revealed and recorded during the ratings should only be reported as AEs if they fulfill the criteria for an SAE or are the reason for discontinuation from treatment with the IP. Please see [Table 4](#) for the timing of evaluations.

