The comparator in this study is placebo (0.9% saline), which will also be administered intravenously. The infusion will be a final volume of 100 mL given at an infusion rate of 1.67 mL/min over 60 minutes. Patients assigned to the placebo treatment group will receive multiple infusions of placebo during the treatment period according to the same schedule as the patients assigned to the AZ6765iv dose groups.

Duration of treatment

Eligible patients will have a screening period of up to 6 weeks. Following the screening period, patients will enter a 12-week double-blind treatment period and a 14-day follow-up period.

Outcome variables:

- **Efficacy**

Primary outcome variable:

- Change from baseline to Week 6 in the MADRS total score

Secondary outcome variables:

- Change from baseline to Week 12 in the MADRS total score
 - Percentage of patients with sustained response, defined as a $\geq 50\%$ reduction from baseline in the MADRS total score at Week 6 and which is maintained through Week 12
 - Change from baseline in the MADRS total score at each scheduled assessment
 - Percentage of responders at each scheduled assessment where responders are defined as patients with a $\geq 50\%$ reduction from baseline in MADRS total score
 - Percentage of patients who are remitted at each scheduled assessment where remission is defined as MADRS total score ≤ 8
 - Change from baseline in functional impairment at each scheduled assessment, as measured by the change from baseline in the SDS total score
 - Change in severity of depressive symptoms at each scheduled assessment as measured by change from baseline in the CGI-S score
 - Change in severity of depressive symptoms at each scheduled assessment as measured by the CGI-I response. Response in CGI-I is based on whether or not the CGI-I score is ≤ 2 (very much improved or much improved).
 - Change from baseline in self-rated severity of depressive symptoms at each scheduled assessment as measured by QIDS-SR-16 total score
- **Safety**
 - Adverse events (AEs)/serious adverse events (SAEs), including their severity
 - AEs leading to treatment discontinuation or study withdrawal

- Suicidality as measured by AEs of suicidality, suicidal ideation, suicide attempts, and suicide completion
- Other significant AEs (OAEs), other AEs of special interest
- Change from baseline in physical examination results, weight, body mass index (BMI), vital signs, clinical laboratory test results, and ECG results

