Worsening symptoms of the primary study condition (ie, MDD) should not be recorded as an AE. However, if hospitalization results from worsening psychiatric symptoms, the hospitalization should be recorded as an SAE in the eCRF.

Study drug abuse is an SAE, even when there are no symptoms or additional AEs, and should be reported according to the guidelines in Section 6.4.4. Misuse of IP is an AE, but is not considered an SAE unless accompanied by serious sequelae.

Should an overdose of IP occur, it must be reported in accordance with the procedures described in Section 13.2. An overdose associated with symptoms must be reported as an AE, while an overdose without associated symptoms, must be reported only on the separate AstraZeneca Clinical Study Overdose Report Form.

Suicidality

Any patient who, based on the investigator's judgment, poses an imminent risk of suicide should be discontinued from the study (see Section 5.8 and Section 5.9). All efforts should be taken to minimize the risk of suicide and the investigator should carefully monitor the

patient. If during the course of the study, a patient shows evidence of serious suicidality (for example warranted by a scoring of 4 or 5 on the C-SSRS), the patient should be referred to their attending psychiatrist, a local emergency room etc. for further evaluation to see if they are safe to continue in the study. The site should have the ability to direct any patient that requires emergency hospitalization to an emergency room or inpatient psychiatric unit that is within a 50 mile radius of the site. In addition, the patient should be able to contact someone at the site 24 hours per day should they have serious worsening of their condition.

Suicide and attempted suicide, irrespective of the method, but occurring in connection with the use of IP, should be reported as AEs (serious or nonserious). This event should be identified as suicide or attempted suicide, and the method of the suicide or attempt should be provided. If an attempted suicide meets the criteria for an SAE, the event must be reported according to the guidelines in Section 6.4.4. Strong suicidal thoughts should also be regarded as AEs.

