All events of suicidality will be carefully monitored. These include events of suicide attempts, suicidal ideation, completed suicides, and suicidal behavior. The last category includes behavioral AEs or SAEs in which the investigator cannot rule out underlying suicidal thinking, eg, motor vehicle accident or behaving in a dangerous or unsafe way, and other self-injurious behaviors.

Investigators are required to provide detailed accounts of AEs related to, or possibly related to, suicidality as described above, to AstraZeneca or representative promptly according to the guidelines for SAEs in Section 6.4.4 and preferably within 5 days for nonserious AEs. Requested information about these events includes the exact nature of the event and the circumstances of the patient at the time of the event. In addition to the usual information required to document AEs or SAEs, data on all of the above will be collected on separate eCRF pages.

The latest version of the AE dictionary, Medical Dictionary for Regulatory Activities (MedDRA), will be used by the CRO staff for the classification and analysis of AEs entered in the study database. For regulatory reporting, SAEs will be processed in the Global Patient Safety Database Sapphire and coded using MedDRA.

Should a pregnancy occur, it must be reported in accordance with the procedures described in Section 13.3, Pregnancy. Pregnancy in itself is not regarded as an AE unless there is a suspicion that an IP may have interfered with the effectiveness of a contraceptive medication.

Causality collection

The investigator will assess the causal relationship (ie, the relationship to study treatment) between the IP and AEs, and answer “yes” or “no” to the question “Do you consider that there is a reasonable possibility that the event may have been caused by the investigational product?”

Causal relationship in cases where the disease under study has deteriorated due to lack of effect will be classified as no reasonable possibility.

For SAEs, causal relationship will also be assessed. Note that for SAEs that could be associated with any study procedure, the causal relationship is implied as “yes.”

A guide to the interpretation of the causality question is found in [Appendix B](#) to the CSP.

Adverse events based on signs and symptoms

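### Sections 6.3.2 and 6.4.3 give opposite instructions on whether nonserious suicidality first found on a rating scale is an adverse event, so the tabulated suicidality AE incidence can be under-counted

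*Protocol*

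**What the plan says.** Section 6.3.2 (Instruments) sets a restrictive rule for findings made during ratings: "Signs and symptoms revealed and recorded during the ratings should only be reported as AEs if they fulfill the criteria for an SAE or". The second exception, which follows in the same sentence, is a finding that leads to IP being stopped. The sentence names no scale. The same section classes the S-STS and CADSS as safety scales, and it counts the C-SSRS and CADSS among the assessments that need rater training: staff "administering the MADRS, HAM-D, C-SSRS, HAM-A, CADSS, CGI-I, and CGI-S, will receive training in conducting these assessments".

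Section 6.4.3 (Recording of adverse events, Suicidality) says "Strong suicidal thoughts should also be regarded as AEs". Suicide and attempted suicide in connection with IP "should be reported as AEs (serious or nonserious"). Detailed accounts of suicidality AEs are requested on separate eCRF pages, with a timeline of their own, "preferably within 5 days for nonserious AEs".

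The Synopsis lists as a safety outcome "Suicidality as measured by AEs of suicidality, suicidal ideation, suicide attempts, and suicide completion". Section 12.2.4 reports the incidence of AEs associated with suicidality and, separately, summarises the STS and C-SSRS by treatment group at each assessment.

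**The concern.** The C-SSRS is the protocol's main structured probe for suicidal ideation and behavior and is given at every scheduled visit. Much of the suicidality detected in the trial may therefore come to light during a rating, which is the situation the 6.3.2 sentence governs. A rater who follows 6.3.2 as written would not report a nonserious, non-discontinuing event as an AE. A rater who follows 6.4.3 would report it if it is an attempt or a strong suicidal thought.

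Two things are at stake. First, the suicidality AE incidence could be too low. Second, with about 60 sites, it could partly reflect which section a site happened to follow. The separate eCRF pages and the nonserious timeline in 6.4.3 might also not be triggered at sites that apply 6.3.2.

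**Working it through.** The protocol has no figure to reproduce here. The check is a comparison of rules, event type by event type.

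| Event | Section 6.3.2 | Section 6.4.3 | Conflict? |
|---|---|---|---|
| Suicidality meeting SAE criteria, found on a scale | AE (first exception) | AE | No |
| Suicidality that is the reason for stopping IP, found on a scale | AE (second exception) | AE if an attempt or strong thoughts | No |
| Nonserious attempt or strong suicidal thoughts, first elicited on a scale, IP continued | Not an AE | AE | **Yes** |
| Suicidal thoughts that are not strong, found on a scale, IP continued | Not an AE | Not made an AE by the sentence on strong thoughts | Not shown |
| Worsening depressive symptoms without hospitalization | Not an AE | Not an AE | No |
| Event volunteered by the patient or given in answer to the open question | Outside the sentence | AE | No |

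The conflict is confined to the third row. It is a realistic case. Section 6.4.3 has a patient who scores 4 or 5 on the C-SSRS referred for evaluation of whether it is safe to continue. A patient who is then judged safe, stays on IP and meets no SAE criterion falls in that row if the thoughts are regarded as strong.

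**How often a rating could reveal such an event.** The C-SSRS row of Table 4 has 17 entries: screening (1), Visits 2 to 16 (15) and the Week 14 follow-up (1). Leaving out screening gives 17 − 1 = 16 administrations per completing patient. These are opportunities for detection. They are not lost events.

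**Which outcome is affected.** The Synopsis and Section 12.2.4 both treat suicidality AEs as something to count, so third-row events belong in that numerator under 6.4.3 and drop out of it under 6.3.2.

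**Dissociation, checked the same way.** The safety objective (Section 2.3) and the Synopsis outcome use CADSS total scores. Section 6.4.3 has no rule specific to dissociation. Table 4 schedules the CADSS at Visits 2 and 13 only, that is at 2 of 15 infusions. The only tension is with the general 6.4.3 instruction to record AEs seen by observation.

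**The case against.** The best counter-argument is that 6.3.2 was never meant for the safety scales. It sits under the heading Efficacy and opens by describing efficacy instruments not covered in 6.2.2. The C-SSRS and S-STS are described in 6.2.2, and the C-SSRS and CADSS again under safety in 6.4.9. Section 6.4 is the dedicated AE section and has its own suicidality rules, which a site could reasonably treat as the more specific instruction. This reading is possible, but the text does not state it: 6.3.2 names the safety scales and carves none of them out. Nor would it remove the problem entirely, because the QIDS-SR-16, which 6.3.2 classes as an efficacy scale, has a suicidal ideation domain (Sections 6.2.2.1 and 11.1.2).

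A second argument is that the bar follows a convention. Section 6.4.3 applies the same serious-or-discontinuation test to protocol-mandated laboratory values and vital signs because these are summarised anyway, and C-SSRS and S-STS results are summarised too. This stands as mitigation, since ideation found on a scale stays visible in the safety results. It does not restore the AE incidence, which is a separate outcome. In addition, the derived C-SSRS occurrence variables in 11.2.6.1 are worded only up to Week 3 of a 12-week treatment period.

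Stronger conclusions that a reader might draw are not supported:

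- **That 6.3.2 contradicts 6.4.3 as a whole.** The two agree that worsening depression is not an AE.
- **That suicidality AEs are suppressed, or that most are lost.** Serious, discontinuing and volunteered events are still reported, the 6.4.3 sentence reaches only strong thoughts, and the protocol gives no basis for a share.
- **That a dissociation AE outcome is equally compromised.** The protocol names no such count, and the CADSS covers few infusions.

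**Conclusion.** The two sections conflict for one defined class of events: nonserious suicide attempts or strong suicidal thoughts, first elicited on a scale, that do not lead to IP discontinuation. Both instructions cannot be followed for that class. The consequence is a possible under-count, or site-dependent recording, of a named and tabulated safety outcome.

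The size is unknown. It depends on how many such events occur, how many of them would otherwise have been volunteered, and which section sites follow, and the protocol gives none of these. The conclusion assumes only that the 6.3.2 sentence is read as written, without an unstated limit to efficacy scales. The protocol gives no reason to expect the under-recording to favor one blinded arm, but a lower recorded incidence in all arms would also shrink any absolute difference between them.

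The point does not touch the primary efficacy analysis. It should be corrected because it affects a safety count and is cheap to settle.

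**What to change.** Reconcile 6.3.2 with 6.4.3 as follows:

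1. Limit the 6.3.2 sentence to symptoms of the depressive illness recorded on the efficacy scales.
2. Add that suicidality events qualifying as AEs under Section 6.4.3 are reported as AEs even when they are found during a rating, on whichever scale.
3. State explicitly whether the 6.3.2 bar applies to symptoms elicited by the CADSS.

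The second item should refer back to 6.4.3 and should not declare all ideation an AE. A blanket rule would bypass the threshold of strong thoughts and clash with the exclusion of worsening depression, since suicidal ideation is itself a criterion symptom of a depressive episode (Appendix F).

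The cost is a short text change, a memo to sites and a modest rise in reported nonserious AEs. No analysis method or sample size changes.

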6.3.2.1 Montgomery-Åsberg Depression Rating Scale (MADRS)

The MADRS is a 10-item scale for the evaluation of depressive symptoms ([Montgomery SA, Åsberg M 1979](#)). The MADRS will be administered by a physician, PhD, RN, or other healthcare professional skilled and experienced in the care of this patient population. Each rater administering the MADRS must receive training and certification on the use of the MADRS and must be approved by AstraZeneca or representative.

Each MADRS item is rated on a 0 to 6 scale. Higher MADRS scores indicate higher levels of depressive symptoms. The individual item scores will be recorded on the eCRF. A patient will be classified as in remission if their MADRS total score is ≤ 8 . The MADRS must be administered at designated visits prior to infusion. The MADRS administered at Visits 3, 4, and 5 (prior to infusions 2, 3, and 4) will evaluate depressive symptoms since last infusion; at all other time points MADRS will evaluate depressive symptoms during the past week regardless of the interval between doses/visits.

6.3.2.2 Sheehan Disability Scale (SDS)

The SDS total score will be calculated as the sum of the score for the 3 inter-correlated domains (school/work, social life, and family life/home responsibilities) and can range from 0 to 30 ([Sheehan KH, Sheehan DV 2008](#)). It is designed for patients to self-rate their level of functional impairment over the last week. The SDS also includes an assessment of lost productivity due to symptoms of illness through 2 items evaluating lost days and under productive days. Each of these 3 items is scored on an 11-point scale, where a score of 0 is “not at all impaired,” 5 is “moderately impaired”, and 10 is “very severely impaired.” A total SDS score will measure total impairment (range (0 to 30)). To calculate the total score, the 3 items within the SDS are summed into a single dimensional measure of functional impairment that ranges from 0 (unimpaired) to 30 (highly impaired). Subscale scores for work, social, and family domains are calculated separately. The subscale numerical ratings range is 0 to 10. Total scores, ranging from 0 to 30, are calculated only for patients who rate all 3 items. The SDS must be administered at designated visits prior to infusion.

6.3.2.3 Clinical Global Impressions: (CGI-S and CGI-I)

The CGI scale is a 3-part, clinician-administered scale that assesses global illness severity and change ([Guy 1976](#)). For the purposes of this study, only the first 2 parts of the scale will be used.

The first part, Severity of Illness (CGI-S), was described above and constitutes 1 of the study inclusion criteria. The second part, Global Improvement (CGI-I), is scored to rate the patient’s change post-treatment.

Each CGI item is scored on a scale from 1 to 7. A CGI-I score of 1 indicates that a patient is “Very much improved” and a score of 7 indicates that a patient is “Very much worse.” The CGI-I is administered at various times during the course of the study to assess patient progress. CGI-I scores greater than 4 indicate worsening, while scores less than 4 indicate improvement.

The CGI-I will be evaluated at designated visits prior to infusion. In addition to examining rating scores, scores will be dichotomized into “Much or Very much improved” (a CGI-I rating ≤ 2), or “Not much improved” (a CGI-I > 2).

6.3.2.4 The Hamilton Scale for Anxiety (HAM-A)

The HAM-A ([Hamilton 1959](#)) is a widely used interview scale that measures the severity of a patient’s anxiety, based on 14 parameters, including anxious mood, tension, fears, insomnia, somatic complaints, and behavior at the interview. Each item is rated on a 5-point scale: 0 (not present) to 4 (severe). At baseline and randomization, this scale provides an indication as to the patient’s level of anxiety, a frequent comorbidity with depression. At subsequent visits, change in level of anxiety will be monitored. The HAM-A must be administered at designated visits prior to infusion.

